6.1.2 Secondary outcomes

- All-cause mortality at ICU discharge, at hospital discharge, and at 6 months.
- Functional independence will be assessed using the FIM. This scale evaluates the amount of assistance required to perform 18 basic daily activities (13 physical and five cognitive components)¹⁵. Each component is scored on a 7-point scale. The final score ranges from 18 to 126, where 18 represents complete dependence and 126 represents complete independence. Deceased patients will be removed for the main analysis.
- Quality of life will be assessed using the Visual Analogue Scale (VAS) of the EQ-5D-5L questionnaire¹⁶. The EQ-VAS is a generic self-assessment instrument for health-related quality of life, for which zero and 100 represent the worst and best imaginable state of health, respectively. Deceased patients will be removed for the main analysis.

- Quality of life will also be assessed using the QOLIBRI questionnaire¹⁷. The scores are reported on a 0-100 scale, with zero being the worst possible quality of life and 100 being the best possible quality of life. Deceased patients will be removed for the main analysis.
- Depression will be assessed using the self-reported PHQ-9¹⁸, which includes nine items that assess the frequency of depressive symptoms in the past 2 weeks. The score lies between zero and 27 with zero being the best outcome and 27 the worst. A threshold value ≥ 10 is generally accepted as the standard for identifying major depression¹⁹. Deceased patients will be removed for the main analysis.

6.1.3 Tertiary outcomes

- The number of red blood cell units transfused in the ICU.
- The lowest daily Hb level recorded in the ICU.
- Infections categorized as any infection, pneumonia, bacteremia, sepsis/septic shock, central nervous system infection. Both the proportion of patients who had an infection and the proportion of patients who had each category of infection.
- The length of time spent on mechanical ventilation in the ICU.
- The length of stay in the ICU.
- The length of stay in the hospital.
- Complications of red blood cell blood transfusions.

6.2 Analysis Methods

All analyses will be performed using the intention to treat principle (see Section 4.3). The main analysis for the primary and secondary outcomes will be adjusted for sex. It will also be adjusted for site, as there are expected variations in TBI mortality between centers, which may be explained in part by regional variations in approaches to discontinuation of life-sustaining therapies²⁰. All treatment effects and differences between groups will be reported with their corresponding 95% CIs. Analyses are summarized in [Table 1](#) and will be reported as outlined in [Appendix 2](#).

6.2.1 Primary outcome analysis

6.2.1.1 Main analysis of the primary outcome:

The null hypothesis states that the proportion of patients with an unfavourable outcome at 6 months, based on a sliding dichotomy of the GOSe score, are equal regardless of the RBC transfusion strategy.

For the main analysis, we will use the sliding dichotomy definition of the primary outcome described in section 6.1. The primary outcome will be analyzed using robust hierarchical Poisson regression, with study site modelled as a random intercept. Risk ratios and absolute risk reduction will be reported. We opted for robust Poisson regression²¹ rather than logistic regression to avoid reporting odds ratios, which systematically overestimate risk ratios and are frequently misinterpreted by clinicians^{22,23}. Our approach to handling missing covariates to determine sliding dichotomy thresholds is outlined in [section 6.3](#). The distribution of GOSe scores will also be presented graphically in the main manuscript (see Figure 1 in [Appendix 2](#)); distributions according to each predicted prognosis tertile will be presented in an online Supplementary Appendix.

6.2.1.2 Sensitivity analyses of the primary outcome:

We will evaluate the robustness of our findings for the main analysis of the primary outcome by conducting sensitivity analyses under various methodological assumptions:

- Multiple imputation. We will use Multiple Imputation by Chained Equations (MICE) for missing covariates, as outlined in [section 6.3](#).
- Complete case analysis. We will only include patients for whom no covariates to calculate the TBI-IMPACT prognostic score were imputed using conditional estimation (see [section 6.3](#)).
- Per protocol analysis. See [section 4.3](#).
- Best case-worst-case scenario. We will include randomized patients with missing primary outcome due to consent withdrawal or loss to follow-up; patients who were randomized by error will not be included in this analysis. In the best-case scenario, patients with missing primary outcomes will be considered as having a favourable outcome if randomized in the liberal strategy and as having an unfavourable outcome if randomized in the restrictive strategy. In the worst-case scenario, patients with missing primary outcomes will be considered as having an unfavourable outcome if randomized in the liberal strategy and as having a favourable outcome if randomized in the restrictive strategy.

6.2.1.3 Additional analyses of the primary outcome:

We will conduct additional analyses of the primary outcome to further assess the reliability of our results. Missing covariates will be handled as outlined in [section 6.3](#).

- Hierarchical proportional odds analysis. The regression model will be adjusted for site (random intercept), sex and admission covariates used in the TBI-IMPACT Prognostic model (age, GCS motor score, pupils, hypoxemia, hypotension, CT classification, tSAH and epidural mass on CT, glycemia and Hb).
- Robust hierarchical Poisson regression model for a dichotomized primary outcome (i.e., unfavourable outcome if the 6-month GOSe is ≤ 4). The model will be adjusted for site (random intercept), sex and admission covariates used in the TBI-IMPACT Prognosis model (age, GCS motor score, pupils, hypoxemia, hypotension, CT classification, tSAH and epidural mass on CT, glycemia and Hb).
- Chi-square test for a dichotomized primary outcome (i.e., unfavourable outcome if the 6-month GOSe is ≤ 4). We will also report a RR.

We will also perform sensitivity analyses of the additional analyses described above (i.e., proportional odds analysis and robust hierarchical Poisson regression model) by including only cases that have no missing covariates (i.e., complete case analysis).

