6.1 Outcome Definitions

6.1.1 Primary outcome

- A sliding dichotomy of the GOSe will be used to assess neurological outcome at 6 months¹⁰. The GOSe comprises eight ranking levels from 1 (death, least favourable outcome) to 8 (upper good recovery, most favourable outcome)³. The sliding dichotomy approach will be based on the International Mission for Prognosis and Analysis of Clinical Trials in TBI (TBI-IMPACT) Core+CT+Lab prognostic model¹¹, which includes the following admission characteristics: age, motor score, pupils, hypoxemia, hypotension, computed tomography (CT) scan classification as defined on the Marshall scale¹², traumatic subarachnoid hemorrhage (tSAH) and epidural mass on head CT scan¹³, glycemia and Hb. Head CT scans results will be adjudicated centrally, using the worst results within the first 24 hours following the injury (see [Appendix 3](#)). For the motor score, we will use the score at emergency department discharge or the score prior to intubation when the patient was intubated in the emergency department. If no motor score was recorded in the emergency department, we will use the first score recorded upon hospital admission, as recommended¹⁴. Hypoxemia and hypotension were recorded in the emergency department, using standardized definitions⁴. For glycemia or Hb, we will use the worst value recorded in the emergency department and, when unavailable, the worst value recorded upon admission. Our approach to handling missing data is outlined in section 6.3.

Patients will then be split into 3 tertiles based on their predicted risk of unfavourable outcome (mortality/vegetative state/severe disability) at 6 months. Patients categorized in the low-risk group will be considered to have an unfavourable outcome if the 6-month GOSe is ≤ 5 (i.e., death, vegetative state, lower and severe disability, or lower moderate disability). Patients in the intermediate risk group will be considered to have an unfavourable outcome if the 6-month GOSe is ≤ 4 (i.e., death, vegetative state, or lower and severe disability). Patients in the high-risk group will be considered to have an unfavourable outcome if the 6-month GOSe is ≤ 3 (i.e., death, vegetative state or lower severe disability).

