6.3 Missing Data

First, every attempt will be made to retrieve any missing data. All frequencies of missing data will be reported. We will not impute data for missing outcomes.

For the main analysis of the primary outcome using sliding dichotomy (see [section 6.2.1.1](#)), we estimate that for each covariate of the TBI-IMPACT prognosis score, around 1% of observations will be missing. In sliding dichotomy analyses, each participant needs to have a unique TBI-IMPACT prognosis score calculated to evaluate the baseline prognosis. Then, in case of missing variables of the TBI-IMPACT score, we will then perform single imputation by conditional estimation³³.

For the sensitivity and additional analyses (see [section 6.2.1.2](#) and [section 6.2.1.3](#)), and for the main analyses of the secondary outcomes (see [section 6.2.2.1](#)), we will use multiple imputation to simulate missing values, assuming that the *missing completely at random* or *missing at random* assumptions are plausible^{14,34}. We will use MICE using the MI and MIANALYZE procedures in SAS (version 9.4) with the number of imputations corresponding to the fraction of missing data³⁵.

Imputation models will include all independent and dependent variables in respective analyses models and any auxiliary variables that may explain the mechanism of missing data (e.g., pupillary reactivity of the contralateral eye when the patient has an ocular prosthesis or had eye/eyelid trauma preventing adequate assessment). We will compare the distribution of observed and imputed values to assess the adequacy of the imputation model³⁶.

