Mortality in the ICU, in the hospital and at 6 months	
 Frailty model¶ 	
 Complete case analysis** 	
 Unadjusted models 	-
FIM (total score, motor and cognition sub-scores)	
 Linear mixed model¶ 	
 Complete case analysis** 	
 Unadjusted models 	-
EQ VAS	
 Linear mixed model¶ 	
 Complete case analysis** 	
 Unadjusted models 	-
QOLIBRI	
 Linear mixed model¶ 	
 Complete case analysis** 	
 Unadjusted models 	-
PHQ-9	
 Linear mixed model¶ Robust hierarchical Poisson regression¶, with a dichotomized PHQ-9 at ≥ 10. 	
 Complete case analysis** 	
 Unadjusted models 	-
Tertiary outcomes				
Number of RBC units transfused per patient in the ICU	Student's t-test		-	-
Lowest daily Hb	Graphically displayed with 95% at each time point		-	-
Infections and transfusion complications	Chi-square test		-	-
Duration of mechanical ventilation	Wilcoxon rank sum test		-	-
Length of stay in the ICU and in the hospital	Wilcoxon rank sum test		-	-

* Adjusted for sex

† Includes only patients for whom no covariate was imputed using conditional estimation to calculate the TBI-IMPACT prognostic score

‡ This population includes all patients within the intention-to-treat group, except those who were allocated to the liberal strategy but were not transfused within a 24-hour time window after reaching Hb ≤ 100 g/L, and those who were allocated to the restrictive strategy but were transfused despite not reaching their transfusion threshold of ≤ 70 g/L, or received more than one unit without reassessing the Hb despite the absence of ongoing important bleeding.

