* The Glasgow Outcome Scale extended (GOSe), measured at 6-month, comprises eight ranking levels from 1 (death, least favourable outcome) to 8 (upper good recovery, most favourable outcome). The primary outcome was centrally assessed by blinded trained personnel.

† The treatment effect is a risk ratio unless otherwise indicated. Confidence intervals have not been adjusted for multiplicity, and inferences drawn from the intervals may not be reproducible.

‡ According to a sliding dichotomy of the GOSe. The sliding dichotomy approach is based on International Mission for Prognosis and Analysis of Clinical Trials in TBI (TBI-IMPACT) Core+CT+Lab prognostic model, which includes admission characteristics (age, motor score, pupils, hypoxemia, hypotension, CT classification, traumatic tSAH on CT, epidural mass on CT, glycemia and Hb). When necessary, we used conditional estimation for missing covariates to calculate an individual TBI-IMPACT score for each patient. Patients will be split into 3 tertiles based on their predicted risk of unfavourable outcome (mortality/vegetative state/severe disability) at 6 months. Patients categorized in the low-risk group will be considered to have an unfavourable outcome if the 6-month GOSe is ≤ 5 (i.e., death, vegetative state, lower and severe disability, or lower moderate disability). Patients in the intermediate risk group will be considered to have an unfavourable outcome if the 6-month GOSe is ≤ 4 (i.e., death, vegetative state, or lower and severe disability). Patients in the high-risk group will be considered to have an unfavourable outcome if the 6-month GOSe is ≤ 3 (i.e., death, vegetative state or lower severe disability). Analyses are adjusted for sex, with a random intercept for site.

§ The complete case analysis includes only patients for whom no covariate to calculate the TBI-IMPACT prognostic score was imputed using conditional estimation.

¶ The per protocol analysis excludes patients who were allocated to the liberal strategy but were not transfused within a 24-hour time window after reaching Hb ≤ 100 g/L, and those who were allocated to the restrictive strategy but were transfused despite not reaching the transfusion threshold of ≤ 70 g/L or received more than one unit without reassessing the Hb despite the absence of ongoing important bleeding.

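### The main primary model uses the IMPACT score to set each patient's GOSe cut-off but leaves it out as a covariate, at a modest and uncertain cost in precision

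*SAP*

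**What the plan says.** SAP section 6.1.1 builds the outcome from the IMPACT Core+CT+Lab model: "Patients will then be split into 3 tertiles based on their predicted risk of unfavourable outcome". The tertile fixes the GOSe cut-off for an unfavourable outcome at ≤5, ≤4 or ≤3 for low, intermediate and high risk.

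Section 6.3 makes the score available for everyone, since "each participant needs to have a unique TBI-IMPACT prognosis score calculated to evaluate the baseline prognosis", and fills missing components by single imputation.

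The main model is described in four places, and they agree:
- Section 6.2.1.1: "The primary outcome will be analyzed using robust hierarchical Poisson regression, with study site modelled as a random intercept".
- Section 6.2: "The main analysis for the primary and secondary outcomes will be adjusted for sex".
- Table 1 legend for the main analysis: "Adjusted for sex".
- Appendix 2, Table 2 footnote: "Analyses are adjusted for sex, with a random intercept for site".

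On reporting, section 6.2.1.1 says: "Risk ratios and absolute risk reduction will be reported". Section 6.2 promises confidence intervals for all effects.

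Elsewhere the IMPACT covariates are standard. For the proportional odds model, section 6.2.1.3 says: "The regression model will be adjusted for site (random intercept), sex and admission covariates used in the TBI-IMPACT Prognostic model". The Poisson model for GOSe ≤4 has the same adjustment, as do all main secondary models (6.2.2.1).

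**The concern.** The model that decides the trial is the only main regression analysis of a primary or secondary outcome without IMPACT adjustment, and the SAP gives no reason. No listed sensitivity analysis adds score or tertile to the sliding-dichotomy model, so a reader could not see what the omission costs.

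Sliding the cut-off uses only part of the score. It can level average risk between tertiles, but patients within a tertile still differ in risk, and the tertile rates become equal only if the GOSe distribution happens to make them so. The remaining prognostic variation stays in the residual and widens the confidence interval of the decisive estimate. At stake is precision, not bias or type I error.

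**Working it through.** **The plan's own figures.** Section 3.3 assumes 40% against 30%, two-sided 5% alpha, 80% power and 1:1 allocation. With pooled variance: n per arm = [1.96·√(2·0.35·0.65) + 0.8416·√(0.40·0.60 + 0.30·0.70)]² / 0.10² = (1.3221 + 0.5646)² / 0.01 ≈ 356, so 712 in total. Section 3.5: 712/0.98² = 741.4, rounded up to 742. Both reproduce. They rest on an unadjusted fixed dichotomy, so this point does not affect them.

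**Inputs to the simulation.**
- From the SAP: GOSe ≤4 of 40% vs 30%; tertile cut-offs ≤5/≤4/≤3; evaluable N = 742 × 0.98 = 727.2, run at 728.
- Assumed, because the SAP does not give them: a common odds-ratio shift; five control distributions for GOSe ≤3/≤4/≤5 (33/40/47, 30/40/50, 26/40/55, 22/40/60 and 15/40/65%); score AUC 0.72, 0.77, 0.81 or 0.85. That makes 5 × 4 = 20 scenarios.
- Model: modified Poisson with robust standard error and sex in every fit; 2,000 runs per scenario under the effect and 1,000 under the null.

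**How far the cut-offs level risk** (control group):

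| ≤3/≤4/≤5 | AUC | low / mid / high tertile |
|---|---|---|
| 33/40/47% | 0.85 | 13 / 35 / 68% |
| 22/40/60% | 0.72 | 38 / 38 / 38% |
| 15/40/65% | 0.72 | 44 / 38 / 27% |

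**Standard error of the log risk ratio relative to the planned model:**

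| Added terms | SE ratio, range over 20 scenarios |
|---|---|
| Score (linear) + tertile indicators | 0.874–0.985 |
| Score (linear) only | 0.885–0.999 |
| Tertile indicators only | 0.897–1.000 |

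Score plus tertiles gained something in every scenario; either one alone can gain almost nothing. When the cut-offs level the tertiles, risk rises within each tertile and drops at each boundary, and a single slope cannot follow that pattern. The empirical standard deviation ratio for score plus tertiles was 0.883–0.989.

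**In patients.** Effective N = 728/ratio². Smallest gain: 728/0.9854² = 750, or 22 more (3%). Largest: 728/0.8742² = 953, or 225 more (31%). At the median gain of about 4%: 728/0.96² = 790, or about 62 more. Power rose by 1.2 to 7.6 points.

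**Validity.** The mean risk ratio differed by at most 0.002. Null rejection averaged 0.049 for the planned model (0.036–0.063) and 0.051 with score plus tertiles (0.038–0.067).

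**Absolute risk reduction.** At least one fitted risk exceeded 1 in 19% to 100% of score-plus-tertile fits, on average in 0.2 to 18 of 728 patients. The risk difference standardised over all patients was unchanged within 0.001, with an SE ratio of 0.874–0.985. With a logistic working model the SE ratio was 0.856–0.983 and null rejection averaged 0.053 (0.041–0.075).

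**Site.** With an assumed 30 sites, SD 0.4 on the logit scale, blocks of 4 and 6 and penalised site intercepts (5 scenarios, 500 runs), the SE ratio was 0.879–0.986, the mean risk ratio agreed within 0.003, and null rejection was 0.036–0.058 planned and 0.038–0.056 adjusted.

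**Cross-check by variance explained.** SE ratio ≈ √(1 − R²), with R² the share of outcome variance explained by score and tertile. With control rates of 32/40/52% and N = 742, simulation (without sex or site) gave:

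| AUC | R² | √(1 − R²) | simulated SE ratio | power without / with |
|---|---|---|---|---|
| 0.680 | 0.035 | 0.982 | 0.984 | 86.5 / 87.1% |
| 0.755 | 0.100 | 0.949 | 0.955 | 86.5 / 90.0% |
| 0.814 | 0.176 | 0.908 | 0.920 | 90.0 / 94.3% |
| 0.863 | 0.267 | 0.856 | 0.877 | 90.2 / 95.7% |

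If the cut-offs fully levelled the tertiles, only the within-tertile R² of about 0.02 to 0.07 would remain, an SE reduction of about 1% to 3.5%.

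**The case against.** Nothing in the main model is misstated or contradicted. The score already enters through the cut-off, which is the design's chosen route to efficiency, and IMPACT-adjusted proportional odds and GOSe ≤4 models are prespecified. The typical gain is small. The top of the range needs a distribution in which adjacent cut-offs differ by only 7 points (33/40/47%) together with an AUC of 0.85. The planned model had about 80% to 96% power when 16 of the scenarios were re-run, so the design target is not compromised. Against that, changing the decisive model after an interim analysis of the primary outcome (3.5), after enrolment ended (3.6) and after version 1.1 of February 2024 (1.2) costs credibility. The adjusted model also brings fitted risks above 1, extra terms in small subgroups such as country (not tested here), and the question of how score and tertile enter the multiple-imputation sensitivity analysis.

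Most of this stands and limits the claim. The plan is valid, the usual gain is nearer 4% than 12%, and timing is the real cost. It does not remove the point: the additional models concern other codings of the GOSe, so no planned analysis shows the sliding-dichotomy effect with the score adjusted for. A labelled sensitivity analysis would show it without the credibility cost.

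**Conclusion.** The concern holds. The main model omits a prognostic score that the trial will hold for every analysed patient, without a stated reason and against the SAP's own practice elsewhere. The consequence is a decisive confidence interval somewhat wider than it needs to be: a standard error larger than necessary by an amount that score plus tertiles would cut by 1.5% to 12.6%, about 4% at the median. Bias and type I error are not at issue.

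The size is of medium certainty. It depends on the GOSe distribution and the score's discrimination in this trial, neither of which is in the SAP, and on the assumptions of a common odds ratio and a score linear on the logit scale. This is an improvement that should be made, not a defect that invalidates the plan.

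**What to change.** **If the randomization code is still closed:**
- Add the IMPACT predicted risk on the logit scale together with the tertile indicators to the main model in section 6.2.1.1, Table 1 and the Appendix 2 Table 2 footnote.
- State how the absolute risk reduction and its confidence interval are obtained, for example by marginal standardisation over all patients.
- State how score and tertile are handled in the multiple-imputation sensitivity analysis, for instance recomputed within each imputed data set.
- Keep the sex-and-site model as a sensitivity analysis. Keep it also for the best-case/worst-case analysis, where patients who withdrew consent may have no usable score (5.2).
- Log the revision in section 1.2 as a dated change made while blinded, not as a clarification.

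**If the code is open:** keep the current main model and add the score-plus-tertile model as a labelled sensitivity analysis of the sliding dichotomy.

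**Cost.** No new data are needed and the risk ratio being estimated is unchanged. The subgroup analyses follow the 6.2.1.1 strategy and would inherit the extra terms. The real cost is changing the decisive model late. If that is judged too high even with the code closed, the labelled sensitivity analysis avoids it.

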6.2.2 Secondary outcomes analyses

6.2.2.1 Main analyses of the secondary outcomes:

All measures in the main analyses of the secondary outcomes will be adjusted for site (random intercept), sex and admission covariates used in the TBI-IMPACT Prognosis model. We will handle missing covariates as described in [section 6.3](#).

- Mortality in ICU, in hospital and at 6 months will be analyzed using frailty models and hazard ratios (HR) will be reported. We will provide Kaplan-Meier curves.

- The total FIM score as well as Motor and Cognition sub-scores will be compared using linear mixed models. We will report means, standard deviations, and the mean difference between groups. If data is not normally distributed, we will report medians with interquartile ranges and use quantile mixed models²⁴ to report difference between groups.
- EQ VAS (visual analogue scale) will be compared using linear mixed models. We will report means, standard deviations, and the mean difference between groups. If data is not normally distributed, we will report medians with interquartile ranges and use quantile mixed models to report difference between groups.
- QOLIBRI will be compared using linear mixed models. We will report means, standard deviations, and the mean difference between groups. If data is not normally distributed, we will report medians with interquartile ranges and use quantile mixed models to report difference between groups.
- PHQ-9 will be compared using linear mixed models. We will report means, standard deviations, and the mean difference between groups. If data is not normally distributed, we will report medians with interquartile ranges and use quantile mixed models to report difference between groups. Also, the proportion of patients with major depression, as defined as a PHQ-9 score greater than or equal to 10¹⁹, will be analyzed using robust hierarchical Poisson regression models^{21,25} and reported using RR.

6.2.2.2 Sensitivity analyses of the secondary outcomes:

We will evaluate the robustness of our findings for the main analysis of the secondary outcomes by conducting sensitivity analyses including only cases that have no missing covariates (i.e., complete case analysis).

6.2.2.3 Additional analyses of the secondary outcomes:

We will report unadjusted analyses for all secondary outcomes.

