|| In the best-case scenario, patients with missing primary outcomes were considered as having a favourable outcome if randomized in the liberal strategy and as having an unfavourable outcome if randomized in the restrictive strategy.

** In the worst-case scenario, patients with missing primary outcomes were considered as having an unfavourable outcome if randomized in the liberal strategy and as having a favourable outcome if randomized in the restrictive strategy.

†† In this category, the treatment effect is an odds ratio. The regression model was adjusted for sex and covariates included in the TBI-IMPACT Prognosis model (age, motor score, pupils, hypoxemia, hypotension, CT classification, traumatic SAH on CT, epidural mass on CT, glycemia and Hb), with a random intercept for site.

‡‡ Unfavourable outcome if the GOSe is ≤ 4 .

§§ The regression model was adjusted for sex and covariates included in the TBI-IMPACT Prognosis model (age, motor score, pupils, hypoxemia, hypotension, CT classification, traumatic SAH on CT, epidural mass on CT, glycemia and Hb), with a random intercept for site

Table 3. Analyses of the Secondary and Tertiary Outcomes.*

	Liberal Strategy (N = xxx)	Restrictive Strategy (N = yyy)	Treatment Effect (95% CI)†
Secondary Outcomes‡			
Mortality — no./total no. (%)§			
In the ICU	xxx/xxx (xx.x)	yyy/yyy (yy.y)	x.xx (y.yy to z.zz)
In the hospital			x.xx (y.yy to z.zz)
At 6-month			x.xx (y.yy to z.zz)
Functional Independence Measure¶			
Overall	999.9±99.9	999.9±99.9	-xx.x (y.y to z.z)
Motor	99.9±99.9	99.9±99.9	-xx.x (y.y to z.z)
Cognitive	99.9±99.9	99.9±99.9	-xx.x (y.y to z.z)
EuroQoL 5-Dimension 5-Level Visual Analogue Scale¶**	99.9±99.9	99.9±99.9	-x.x (y.y to z.z)
Quality of Life after Brain Injury¶††	99.9±99.9	99.9±99.9	-x.x (y.y to z.z)
Patient Health Questionnaire-9¶‡‡	99.9±99.9	99.9±99.9	-x.x (y.y to z.z)
Tertiary Outcomes§§			
Number of red blood cell units transfused per patient¶¶¶¶	9.9±9.9	9.9±9.9	-x.x (y.y to z.z)
Infection — no./total no. (%)			
Any			-x.x (y.y to z.z)
Pneumonia			-x.x (y.y to z.z)
Bacteremia			-x.x (y.y to z.z)
Sepsis/septic shock			-x.x (y.y to z.z)
Ventriculitis/meningitis/brain abscess			-x.x (y.y to z.z)
Transfusion reactions — no./total no. (%)¶¶***			-x.x (y.y to z.z)
Median duration of mechanical ventilation — days (interquartile range)¶	9.9 (0.0 to 9.9)	9.9 (0.0 to 9.9)	x.xx (y.yy to z.zz)
Median length of ICU stay — days (interquartile range)¶	9.9 (0.0 to 9.9)	9.9 (0.0 to 9.9)	x.xx (y.yy to z.zz)

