Median length of hospital stay — days (interquartile range)¶	9.9 (0.0 to 9.9)	9.9 (0.0 to 9.9)	x.xx (y.yy to z.zz)

* Plus-minus values are means ±SD.

† Confidence intervals have not been adjusted for multiplicity, and inferences drawn from the intervals may not be reproducible.

‡ Secondary outcomes were centrally assessed by blinded trained personnel. All analyses are adjusted for site (random intercept), sex and admission covariates used in the TBI-IMPACT Prognosis model (age, motor score, pupils, hypoxemia, hypotension, CT classification, traumatic SAH on CT, epidural mass on CT, glycemia and Hb)

§ In this category, the treatment effect is a hazard ratio.

¶ In this category, the treatment effect is the between-group difference.

|| The Functional Independence Measure scale evaluates the amount of assistance required to perform 18 basic daily activities (13 physical and five cognitive components). Each component is scored on a 7-point scale. The final score ranges from 18 to 126, where 18 represents complete dependence and 126 represents complete independence. Patients who died or with missing data were excluded (xx in the Liberal Strategy and yy in the Restrictive Strategy).

** The EuroQoL 5-Dimension 5-Level Visual Analogue Scale is a generic instrument for health-related quality of life, for which zero and 100 represent the worst and best imaginable state of health, respectively.

†† The Quality of Life after Brain Injury Scale is a TBI-specific instrument for health-related quality of life, for which zero and 100 represent the worst and best imaginable state of health, respectively.

[figure not shown]
‡‡ Patient Health Questionnaire includes nine items that assess the frequency of depressive symptoms in the past 2 weeks. The score lies between zero and 27 with zero being the best outcome and 27 the worst.

§§ Tertiary outcomes were assessed locally by unblinded trained research personnel using standardized definitions.

¶¶ From the randomization to the ICU discharge

||| In this category, the treatment effect is a risk ratio

*** Detailed description of transfusion reactions is provided in the Supplementary Appendix.

Figure 2. Levels on the Glasgow Outcome Scale-extended at 6 Months.

Appendix 3

Interpretation of head CT scans results

We used a rigorous 3-step approach to ensure a robust and unbiased assessment of head CT scans.

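### ICU and in-hospital mortality are given a frailty-model hazard ratio with no rule for patients discharged alive, so the estimate need not be the effect on the outcome as defined

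*SAP*

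**What the plan says.** - **Definition (SAP 6.1.2):** "All-cause mortality at ICU discharge, at hospital discharge, and at 6 months".
- **Analysis (SAP 6.2.2.1):** "Mortality in ICU, in hospital and at 6 months will be analyzed using frailty models and hazard ratios (HR) will be reported". The next sentence is "We will provide Kaplan-Meier curves", without saying for which of the three outcomes. Table 1 has a single row, "Mortality in the ICU, in the hospital and at 6 months", with a frailty model as the main analysis.
- **Reporting (Appendix 2, Table 3):** the rows are headed "Mortality — no./total no" with percentages, and the footnote says "In this category, the treatment effect is a hazard ratio".
- **Sensitivity and additional analyses (6.2.2.2, 6.2.2.3):** complete cases on covariates, and unadjusted versions.

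The SAP gives no censoring rule, follow-up horizon or competing-risk method for the ICU and hospital models. Section 6.3 deals with missing data only.

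**The concern.** A patient who leaves the unit alive can no longer die in it. A survival model for in-unit death therefore needs a rule for discharge alive, and that rule decides what the HR estimates:

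- **Censored at discharge:** the HR compares daily death rates among patients still in the unit (a cause-specific HR). It does not reflect how long patients stay exposed to that rate.
- **Kept at risk to a fixed day:** the HR follows the proportion who die in the unit.

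Two analysts who both follow the SAP could report different HRs. Under the first rule, the HR can also disagree with the counts in its own row when time to discharge differs between arms. None of the planned sensitivity or additional analyses would show this.

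Two of the three mortality time points are affected. Analysts are blinded to allocation (SAP 3.2), so the issue is what the estimate means, not a choice made to favour an arm.

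**Working it through.** The SAP gives no figure for these mortality analyses, so there is none to reproduce. The rates below are assumptions. Only the 742 patients (SAP 3.5) and 1:1 allocation (SAP 3.2), hence 371 per arm, come from the document. Covariates and the site frailty are left out.

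**Model.** Constant daily hazards of death (d) and of discharge alive (r):

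- in-unit mortality = d/(d + r)
- mean stay = 1/(d + r)
- so RR = (d₁/d₀) × (mean stay, liberal / mean stay, control)

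The risk ratio is thus the cause-specific HR multiplied by the ratio of mean stays. The two are equal only if mean stay is equal.

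**Main example.** Control d = 0.02 and r = 0.08 per day, giving 20% mortality and a 10-day stay. Liberal d = 0.018 (death HR 0.90), with r varied:

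| Discharge HR | r | Mean stay, liberal (days) | Mortality, liberal | RR | Risk difference (points) | HR, discharge censored | HR, at risk to day 180 |
|---|---|---|---|---|---|---|---|
| 1.00 | 0.080 | 10.2 | 0.018/0.098 = 18.4% | 0.92 | -1.6 | 0.90 | 0.91 |
| 0.95 | 0.076 | 10.6 | 0.018/0.094 = 19.1% | 0.96 | -0.9 | 0.90 | 0.95 |
| 0.90 | 0.072 | 11.1 | 0.018/0.090 = 20.0% | 1.00 | 0.0 | 0.90 | 1.00 |
| 0.85 | 0.068 | 11.6 | 0.018/0.086 = 20.9% | 1.05 | +0.9 | 0.90 | 1.05 |
| 0.80 | 0.064 | 12.2 | 0.018/0.082 = 22.0% | 1.10 | +2.0 | 0.90 | 1.10 |

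The censored HR is 0.90 by construction. The last column is a Cox fit to 400,000 simulated patients per arm; a numerical large-sample solution agrees to within 0.01.

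**Other control mortality, death HR 0.90.** At 15%, the RR is 0.95 (discharge HR 0.95; 0.955 unrounded) and 1.10 (discharge HR 0.80). At 25%, it is 0.96 and 1.09.

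**Death hazard unchanged (HR 1.00), control 20%.** For discharge HR 0.95, 0.90, 0.85 and 0.80, the RR is 1.04, 1.09, 1.14 and 1.19.

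**Precision at discharge HR 0.80.**

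- Deaths = 371 × (0.200 + 0.2195) = 156. SE(log HR) = 2/√156 = 0.160, so HR 0.90 has a 95% CI of 0.66 to 1.23.
- SE(log RR) = √[0.7805/(371 × 0.2195) + 0.8/(371 × 0.2)] = 0.143, so RR 1.10 has a 95% CI of 0.83 to 1.45.

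**Kaplan-Meier, only if a curve for in-unit death is drawn with discharge censored.** At day 28 with 20% mortality, 1 - KM = 1 - exp(-28d) and the cumulative incidence is 0.20 × (1 - exp(-28/stay)). This gives 43% v 19% (10-day stay), 33% v 17% (14-day) and 24% v 15% (20-day).

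**The case against.** - **Nothing is contradicted.** Counts beside an HR are ordinary reporting, and a cause-specific HR is a valid quantity. This stands. The gap is that the SAP neither names that quantity nor states the rule that would produce it.
- **The harm is conditional.** It needs censoring at discharge and a difference in time to discharge, which the SAP does not predict; it compares stay only as a descriptive tertiary outcome (6.2.3). With equal discharge rates the figures are 0.90, 0.91 and 0.92, and with patients kept at risk the HR follows the RR throughout. This stands and limits the size. It does not tell the analyst which rule to use.
- **The risk ratio has its own weakness.** It moves to between 1.04 and 1.19 when only discharge slows, where the cause-specific HR correctly shows 1.00. This also stands. The case for the risk ratio is that it answers the outcome as defined in 6.1.2.
- **The reader can see the discrepancy.** Counts, length of stay and 6-month mortality all appear in Appendix 2 Table 3. That helps, but the crude counts do not give the adjusted estimate that the SAP promises.
- **It is late.** Version 1.1 is dated February 2024 and describes its edits as clarifications (SAP 1.2). Changing the effect measure is more than a clarification and must be recorded as a change.

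**Conclusion.** The concern holds. For ICU and in-hospital mortality the SAP does not fix what the HR estimates, and under the usual censoring it is not the effect on the outcome that 6.1.2 defines. In the worked example an HR of 0.90 goes with a risk ratio of anything from 0.92 to 1.10. The direction reverses only if discharge is slowed proportionally more than death is reduced, here a mean stay above 11.1 days. At 742 patients the intervals overlap widely, so the difference is in the estimate, not in significance.

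The size rests on assumed mortality, stay and hazard ratios, and on constant hazards. That the two rules target different quantities does not. The Kaplan-Meier point applies only if in-unit curves are drawn with discharge censored. Because only two secondary outcomes are involved, this is something that should be corrected, not a threat to the trial's main conclusion.

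**What to change.** In 6.2.2.1, Table 1 and the ICU and hospital rows of Appendix 2 Table 3:

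1. Analyse ICU and in-hospital death as binary outcomes with the adjusted robust hierarchical Poisson model. Under 6.2.2.1 the proportion with PHQ-9 ≥ 10 already "will be analyzed using robust hierarchical Poisson regression models". Use the same covariates and random intercept for site.
2. Report the risk ratio and risk difference with 95% CIs, in line with the primary outcome (6.2.1.1: "Risk ratios and absolute risk reduction will be reported").
3. State how patients still in the ICU or hospital at 6 months are counted.
4. Restrict the frailty-model HR and Kaplan-Meier curves to 6-month mortality. For any in-unit curve, use cumulative incidence with discharge alive as a competing event.
5. If an in-unit HR is kept as a supplement, state how discharge alive is handled and, if it is censored, label the HR cause-specific.

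The cost is wording: no new data, and a model the SAP already contains. The change should be entered in the revision table (1.2) as a change of analysis and dated before the randomization code is opened. The downside is small: because the risk ratio also reflects length of stay, it should be read beside the length-of-stay and 6-month mortality results.
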